### 535 **Affective Well-Being Measures**

536 **1. Depression Episodes** will be operationalized in a manner consistent with other studies in  
537 perimenopausal depression and based on the following assessments: **The Center for**  
538 **Epidemiologic Studies Depression scale (CES-D)** is a 20-item self-report form assessing  
539 depressed mood. CES-D scores  $\geq$  16 have been consistently validated as defining high  
540 depressive symptoms suggestive of clinically significant DEP (positive predictive value=75%),  
541 and this cut-point has been used to define depressive episodes in multiple perimenopausal  
542 samples. Moreover, elevated CES-D scores have been shown to be sensitive to the anti-  
543 depressant actions of ERT in PM women. **Thus, CES-D scores  $\geq$  16 will be used to**  
544 **operationally define ‘depression episodes’.** However, if CES-D scores are  $>$  10 at any study  
545 visit then the Structured Clinical Interview for DSM-IV (non-patient edition) will be

546 administered to determine the presence of either minor or major depression. **Functional**  
547 **Impairment:** We will use the widely used Medical Outcomes Study 36-item short form (SF-  
548 36), which yields scores of general health perceptions, physical functioning, role limitations due  
549 to physical functioning, social functioning, bodily pain, general mental health, role limitations  
550 due to emotional problems, and vitality. The rationale for the selection of this instrument is  
551 based on: 1) the demonstration that it is sensitive to change over time; 2) its incorporation of  
552 subscales to specifically assess functional impairment related to emotional and physical  
553 symptoms as well as overall social functioning; 3) its able to discriminate subgroups of CVD  
554 patients known to have poorer survival and worse disease; and 4) normative data for this scale  
555 are available for the general US population as well as 13 medical conditions. **Symptom**  
556 **Severity and Affective Instability** will be assessed with the CES-D scale (at baseline and  
557 months 2,4,6,8,10 and 12), the former with a repeated measures approach and the latter by the  
558 variance in the CES-D score over 12 months.

559 **Lifetime Trauma Exposure** will be assessed by a validated interview. A cumulative (total)  
560 trauma score will be generated by assigning one-point for each of the following 15 traumas: **1)**  

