755 that it is medically necessary to become unblinded to treatment assignment, he will be able to do  
756 so very quickly.

757 We also have a plan for the monitoring of medical conditions that may emerge during the course  
758 of the 12 month study requiring treatment or withdrawal. The development of hypertension or  
759 hyperlipidemia represent the most likely medical conditions that may emerge over a 12 month  
760 interval in perimenopausal women. Our protocol allows for the frequent monitoring of BP levels  
761 (months 1, 2, 4, 6, 8, 10, and 12) throughout the protocol. Consistent with JNC 7 guidelines, the  
762 detection of BP levels during the study in the Stage 1 HTN range (140 – 159 mmHg SBP or 90 –  
763 99 mmHg DBP) will prompt monthly reassessments of BP to confirm BP status, and a review of  
764 the American Heart Association (AHA) dietary and physical activity guidelines with the subject.  
765 If the average BP over any 3 consecutive months remains in the Stage 1 HTN range, the subject  
766 will be withdrawn and referred for treatment. Detection of BP levels consistent with Stage 2  
767 HTN at any point will prompt immediate withdrawal and referral. Fasting LDL cholesterol will  
768 be measured at months 6 and 12 (Time 1 and 2 testing). However, in women with LDL-  
769 cholesterol > 190 mg/dl at month 6, a level for which the NCEP recommends therapeutic  
770 lifestyle changes and LDL-lowering drugs, we will re-assess fasting lipid profiles at months 8  
771 and 10. Should LDL again exceed 190 mg/dl on either determination, the subject will be  
772 withdrawn from the study and referred for treatment. If a subject develops coronary heart  
773 disease, venous thromboembolism, breast or endometrial or ovarian cancer, or biliary tract  
774 disease, she will be withdrawn from the study. Our plan to enroll only medically healthy  
775 perimenopausal women and to educate, encourage, and assess compliance with the AHA diet  
776 and exercise guidelines will minimize the development of medical conditions requiring  
777 withdrawal.

778 **General Statistical Considerations:** This is a two between subjects and one within-subjects  
779 (repeated measure) design. The two between-subjects factors are treatment (ERT or placebo,  
780 randomized) and history of DEP (positive or negative, non-randomized), and the within-subjects  
781 factor is time (psychiatric outcomes at months 0 (baseline), 1, 2, 4, 6, 8, 10, and 12, and CV  

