782 measures at months 0, 6, 12). Analyses which use outcomes measured repeatedly will use this  
783 repeated measures design for analysis, with mixed models for continuous outcomes and logistic  
784 models for categorical outcomes. The mixed models we will fit will be random coefficient  
785 models, which treat the time variable as numerical. We do this for several reasons: (1) it allows  
786 for a finer assessment of precisely when women come in for a “visit,” as visits rarely take place  
787 on exactly the day planned, and (2) the covariance structure is necessarily simpler, leading to  
788 more efficient mixed models. For comparisons assessing change over time, we will assess this  
789 change as a difference between treatments or groups, as stated with respect to specific  
790 hypotheses, on differences between baseline and month 12 least squares means (LSMs). The  
791 month 6 CV data will be part of the mixed model predicting the 12 month least squares means.  
792 That is, the mixed model is an Intent- to-Treat analysis which uses all available data to make a  
793 prediction about what outcomes we would see if all subjects had remained in through the 12  
794 month endpoint. Several outcomes are measured or derived only once over the follow-up period  
795 (e.g., presence of at least one depressive episode during follow-up, or affective instability during  
796 the follow-up period). For those outcomes, the model will not include a repeated factor, and will  
797 be a two-factor ANOVA or logistic regression. For each analysis, where appropriate, we will  
798 perform sensitivity analyses by adding potential mediators, moderators, or confounders (see

799 D.4.3.) in an appropriate way to the model to assess the effect of these confounders, and to better  
800 define mechanisms, and subjects for whom, for example, treatment is effective. Most  
801 hypotheses will be examined as main effects, interactions, or contrasts. Prior to statistical  
802 analyses, we will use descriptive statistics and graphics to screen the data for errors, outliers, and  
803 potential influential observations, and to check distributional assumptions. We will not blindly  
804 switch to non-parametrics if distributions within groups do not appear to be normal, but will  
805 judge whether the type and degree of non-normality are such which require rethinking our  
806 modeling assumptions. We have a relatively large sample size and our linear models should be  

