906 parallel effects on metabolic risk (via a logistic regression), baroreceptor sensitivity, and flow  
907 mediated dilatation. Hypothesis H1B involves partitioning the interaction effect in these models.

908 **Aim 3 Hypothesis 2:** This will be examined in a logistic regression model with two between-  
909 subjects factors (DEP history and treatment) and the emergence of at least one DEP episode as  
910 the response. This is the treatment main effect in the model. If we reject the null hypothesis, we  
911 will examine the same hypothesis using CED-D total (mixed model), functional impairment  
912 (mixed model), number of episodes (Poisson regression), and affective instability (mixed model).

913 **Aim 3 Hypothesis 3 (secondary):** This hypothesis will use a logistic regression model with two  
914 between-subjects factors as above, the emergence of at least one DEP episode as the response,  
915 and stress reactivity in the model as a mediator.

916

917 **POWER AND SAMPLE SIZE CALCULATIONS FOR EACH SPECIFIC AIM:**

918 It is not feasible to conduct power analyses for every hypothesis. While this is a mechanistic  
 919 study designed, in part, to examine mediators of E2's beneficial effects on CV risk and DEP, we  
 920 must first be able to detect a beneficial effect of E2. Thus, we conduct power for Aim 3, H2.  
 921 We also felt it important, however, to confirm we are powered to detect meaningful differences  
 922 in the Stress Reactivity composite score since it is our primary CV outcome variable and also a  
 923 predicted mediator.

924 **Aim 3 Hypothesis 2:** Based on the work of Freeman et al (Menopause, 2009. **16**(4): p. 728-34)  
 925 for rates in untreated women, and our prediction that ERT will cut the rate of depression by 50%  
 926 (a clinically relevant difference), we predict the following percentages of women will experience  
 927 at least one DEP episode during the follow-up in our groups:

928

		Treatment Assigned	
		ERT	Placebo
Depression	Positive	22.5	45
History	Negative	15	30
(Combined)		(18.75%)	(37.5%)

929

930 The hypothesis corresponds to using logistic regression to test the depressive episode rate  
 931 between all those treated with ERT (18.75%) versus those treated with placebo (37.5%). Using a  
 932 logistic regression with this effect size, a two-tailed significance level of 0.05, and 240 total  
 933 subjects, power exceeds 96%. Further, power should be higher for the parallel poisson  

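### The ever-depressed endpoint is tested by a once-per-woman logistic regression that takes no account of follow-up, so the Aim 3 H2 test is biased if loss to follow-up differs between arms

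*Protocol*

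**What the plan says.** **Endpoint and model.** General Statistical Considerations lists outcomes obtained once over follow-up: "e.g., presence of at least one depressive episode during follow-up, or affective instability during" follow-up. It then says "For those outcomes, the model will not include a repeated factor, and will" be a two-factor ANOVA or logistic regression. The Data Analytic Plan applies this to Aim 2 H2 and to Aim 3 H2, the main treatment test for depression. Aim 3 H2 has "subjects factors (DEP history and treatment) and the emergence of at least one DEP episode as" the response. Affective Well-Being Measures defines an episode as a CES-D score of 16 or more.

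**Early exit.** Monitoring and Reporting of Adverse Events ends participation for several conditions:
- A woman whose blood pressure stays in the Stage 1 range over a three-month average "will be withdrawn and referred for treatment".
- Stage 2 blood pressure leads to immediate withdrawal.
- LDL above 190 mg/dl at month 6 and again at month 8 or 10 leads to withdrawal.
- Coronary heart disease, venous thromboembolism, certain cancers or biliary disease lead to withdrawal.

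**Missing follow-up.** The only argument on incomplete follow-up is that "the mixed model is an Intent- to-Treat analysis which uses all available data to make a" prediction for the case where everyone stayed to month 12. It is made for the mixed models and not for the binary endpoint.

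**Schedule.** Affective Well-Being Measures gives CES-D at baseline and "months 2,4,6,8,10 and 12), the former with a repeated measures approach". General Statistical Considerations says the within-subjects "factor is time (psychiatric outcomes at months 0 (baseline), 1, 2, 4, 6, 8, 10, and 12, and CV" measures at months 0, 6 and 12. The first list omits month 1 and the second includes it.

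**The concern.** An episode can be recorded only at an assessment the woman attends, so the chance of a yes rises with the number of visits. The logistic model gives a woman seen three times the same standing as one seen seven times. If the arms lose women at different rates, the treatment coefficient mixes the effect on mood with the difference in observation.

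The protocol gives grounds for unequal loss in either direction. Its risk section lists raised blood pressure as a less frequent estradiol side effect. Its hypotheses predict lower metabolic risk on ERT, and blood pressure is one component of metabolic risk.

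The supporting analyses do not protect the test. The Poisson model of episodes per month is only a sensitivity analysis, and only in Aim 2. In Aim 3 the Poisson and CES-D models run only after the logistic test has rejected, so they can neither recover a missed effect nor prevent a false one.

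**Working it through.** **Inputs from the protocol.** Episode rates of 18.75% (ERT) and 37.5% (placebo); two-tailed 0.05; 320 randomized 1:1, so 160 per arm; seven post-baseline visits (months 1, 2, 4, 6, 8, 10, 12).

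**Assumptions.** Dropout is not stated, so a range is shown. Its centre of 25% would match 240/320 = 75%, but the protocol does not say that the 240 in its power statement means completers. The per-visit risk is constant. Leavers are spread evenly over 0 to 6 attended visits. Leavers without a recorded episode count as episode-free.

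**The plan's own figure.** A two-proportion test of 18.75% against 37.5% gives 90.3% power with 240 women and 96.5% with 320. The stated power above 96% therefore matches 320, not the 240 named. That is a separate matter and does not decide this point.

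**Step 1: per-visit risk.** h = 1 − (1 − 0.375)^(1/7) = 0.0649. The chance of a recorded episode after k visits is 1 − (1 − h)^k: 18.2% after three visits and 37.5% after seven. The mean over k = 0 to 6 is 0.175.

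**Step 2: observed rate with dropout d, no treatment effect.** Observed = (1 − d) × 0.375 + d × 0.175. At 35%/15% (ERT/placebo):
- ERT: 0.65 × 0.375 + 0.35 × 0.175 = 0.305
- Placebo: 0.85 × 0.375 + 0.15 × 0.175 = 0.345

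This is a spurious difference D of 4.0 points.

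**Step 3: rejection rate.** For the pooled z-test, SE0 = √(2 × 0.325 × 0.675/160) = 0.0524 and SE1 (unpooled) = 0.0523. Rejection = Φ[(D − 1.96·SE0)/SE1] + Φ[(−D − 1.96·SE0)/SE1] = Φ(−1.20) + Φ(−2.73), or about 11.9%.

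| Dropout ERT/placebo | Observed ERT | Observed placebo | Rejection, no true effect |
|---|---|---|---|
| 25%/25% | 32.5% | 32.5% | 5.0% |
| 30%/20% | 31.5% | 33.5% | 6.7% |
| 35%/15% | 30.5% | 34.5% | 11.9% |
| 40%/10% | 29.5% | 35.5% | 20.8% |

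**Step 4: excluding episode-free leavers instead (35%/15%).** ERT: 0.305/(0.65 + 0.35 × 0.175) = 42.9%. Placebo: 0.345/(0.85 + 0.15 × 0.175) = 39.4%. Both exceed 37.5%, and the bias now runs against ERT.

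**Step 5: late leavers.** An LDL withdrawal cannot occur before month 8, that is, after five or six visits. Averaging k = 5 and 6 gives (0.285 + 0.332)/2 = 0.308. At 35%/15% the observed rates are 35.2% and 36.5%, and rejection is 5.7%.

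**Step 6: simulation check.** Constant monthly hazards for episode and dropout were used, with episodes detected at the next scheduled visit (4,000 runs with no effect, 2,000 at the design effect). A visit-stratified log-rank test stood in for a discrete-time model of first episode.

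| Scenario | Dropout ERT/placebo | Binary test | First-episode test |
|---|---|---|---|
| No effect | 25%/25% | 5.9% | 5.9% |
| No effect | 30%/20% | 7.5% | 4.9% |
| No effect | 35%/15% | 13.8% | 4.8% |
| No effect | 40%/10% | 25.4% | 5.8% |
| Design effect (power) | 25%/25% | 93.6% | 94.8% |
| Design effect (power) | 15%/35% | 76% | 94% |

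**The case against.** The strongest reply is that the handling of withdrawn women usually belongs in the SAP, which is not at hand, and that the protocol nowhere says leavers are coded episode-free. The second half of that stands, and a coding rule cannot be attributed to the plan. But the protocol does fix the model, which is presence or absence per woman with no follow-up term. Under that model, counting leavers as episode-free and excluding them give opposite biases.

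Three further points stand. Equal dropout does not inflate the type I error. The marked inflation needs imbalances of 20 to 30 points, which nothing in the protocol predicts. Some triggers act late: LDL withdrawals come after five or six of the seven visits, where the distortion nearly disappears. The protocol also aims to limit medical withdrawals through its eligibility criteria and its diet and exercise advice.

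Some stronger readings are tempting and not supported:
- **That the plan favours ERT.** If ERT improves blood pressure as hypothesised, placebo would lose more women and a benefit would be hidden.
- **That the withdrawal triggers are all trial outcomes.** Blood pressure enters metabolic risk; LDL does not.
- **That the episode grid has only six visits.** The list without month 1 describes symptom severity and affective instability, while other sections assess depressive symptoms at month 1. It is a schedule to reconcile and does not show a lower expected episode rate.
- **That the intent-to-treat label is part of this fault.** It describes the mixed models, which do not analyse this endpoint.

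**Conclusion.** The point holds as a cheap improvement. The protocol fixes an analysis of the ever-depressed endpoint that ignores how long each woman was observed, in a design that removes some women early. If follow-up differs by arm, the Aim 3 H2 test is biased, and the direction depends on which arm loses more women and on how leavers are handled. Under the stated assumptions the false-positive rate runs from the nominal 5% with equal dropout to about 12% at 35%/15% and 21% at 40%/10%. It stays close to 5% if women leave late. The dropout rates, the constant risk and the spread of leavers are assumptions, so these figures show sensitivity and are not a forecast for this trial. Aim 2 H2 uses the same model and has the same weakness if women with and without a depression history leave at different rates.

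**What to change.** Make the primary analysis of Aim 3 H2, and of Aim 2 H2, a discrete-time model of first episode: complementary log-log regression on woman-visits up to the first episode or the last CES-D, with treatment, depression history and visit as terms. Report 12-month cumulative incidence by arm. Keep the planned logistic regression as a sensitivity analysis, with a stated rule for women who leave without an episode. Reconcile the CES-D schedule in Affective Well-Being Measures with the one in General Statistical Considerations. Leave the withdrawal rules as they are.

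The cost is analysis wording only. The data are already collected, and the simulation showed no loss of power at equal 25% dropout. The drawback is that the model assumes non-informative censoring. Withdrawals should therefore be reported by arm and reason, with a sensitivity analysis for withdrawal related to mood or blood pressure.

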### 478 **MEASUREMENTS**

#### 479 **Cardiovascular Risk Measures**

480**1) Metabolic Risk:** We will employ National Cholesterol Education Program (NCEP) standard  
481 criteria for determining the Metabolic Syndrome based on blood pressure (BP) levels, abdominal  
482 obesity, and fasting triglyceride, HDL and glucose. For **BP:** subjects will be seated for 5 mins  
483 with arm supported at heart level. The auscultatory method will be used, employing a hand  
484 aneroid sphygmomanometer and stethoscope placed over the brachial artery at the inside of the  
485 elbow. A minimum of two BP measurements will be taken at least 5 mins apart and averaged to  
486 determine BP. **Waist Circumference** will be measured using the NHANES III Protocol . The  
487 subject stands and the examiner palpates the upper hip bone to locate the right iliac crest to  
488 determine the mid-axillary line. The measuring tape is placed in a horizontal plane around the  
489 abdomen at this point and the measure is made at a normal minimal respiration. Following an  
490 overnight fast, blood will be sampled for **fasting triglycerides and HDL** (see assay descriptions  
491 below). We will also use **Insulin Sensitivity/Resistance to assess metabolic risk** using  
492 Homeostasis Model Assessment (HOMA) beta-cell index derived from a single fasting sample of  
493 glucose and insulin levels. This is the most widely used surrogate measure of insulin resistance  
494 (IR). Fasting HOMA-IR levels have been shown in large scale studies to predict CV events even  
495 after adjustment for other traditional risk factors. We will use the standard calculation for  
496 HOMA-IR, which is fasting insulin (uU/ml) times fasting glucose (mmol/l) divided by 22.5.  
497 Homa-IR has been validated in normoglycemic subjects against insulin sensitivity measured  
498 directly from the euglycemic-hyperinsulinemic clamp technique. Subjects will be considered  
499 insulin resistant on the basis of HOMA-IR > 3.2, consistent with other investigations.

500

501 **Metabolic Risk will be assessed at baseline, month 6 and month 12. Subjects will be**  
502 **classified as having metabolic risk if they either:** 1) meet standard NCEP criteria for  
503 metabolic syndrome based on any three of the following risk factors: (1) BP  $\geq$ 130/  $\geq$ 85 mmHg,  
504 (2) waist circumference  $>$  88 cm, (3) triglycerides  $\geq$  150 mg/dl, (4) HDL cholesterol  $<$  50 mg/dl,  

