#### 579 **Risks and Measures to Minimize Risks**

580 The most likely risks involve side effects associated with the use of reproductive hormones  
581 (estradiol or progesterone).

582 The most frequent side effects associated with estradiol use include edema, breast tenderness,  
583 and changes in appetite and weight. Less frequent side effects include jaundice, nausea,  
584 abdominal cramps, increased blood pressure, headache and worsening of migraines or asthma,  
585 depression, nervousness, acne, cystitis-like syndrome, enlargement of uterine fibroids,  
586 intolerance to contact lenses and dizziness. Skin rash or irritation may also occur at site where  
587 the patch (containing estrogen) is placed. Progesterone - The most common side effects

588 associated with progesterone include breast tenderness, dizziness, abdominal bloating, vaginal  
589 discharge, chest pain, and diarrhea. Less common side effects include headache, dizziness,  
590 breast pain, musculoskeletal pain, and viral infection

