807 robust to relatively mild violations of normality. Even so, in the event we decide that the linear  
808 or linear mixed models we've selected are not appropriate, we will examine the possibility of  
809 testing hypotheses using permutation tests, sampling from the permutation distribution, in  
810 preference to non-parametrics.

811 We will define *affective instability* as the variance of each subject's CED-D total score over her  
812 follow-up period. We define the CV risk variable *Stress Reactivity*, as a composite formed in the  
813 following way: for IL-6, Mean Arterial Pressure, Vascular Resistance, and Cortisol, we will  
814 form the difference between resting and stress measures, yielding *reactivity* for each measure.  
815 We will calculate mean and SD for each measure at baseline (pre-treatment) and use those to  
816 standardize each measure at baseline (pre-treatment) and during the intervention to a common  
817 scale. We will then add the z-scores for the 4 measures together to form our stress reactivity  
818 composite at each point measured.

819 **Multiple Testing:** Several of the hypotheses use multiple outcome measures. We have in each  
820 identified one outcome as the primary outcome variable, and testing on this variable will be done  
821 without correction for multiple comparison. We will only examine other variables if the null  
822 hypothesis is rejected for the primary outcome variable. This enables us to follow significant  
823 effects with other analyses to explain or refine the response, helping us interpret the results.

824

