853 **affective well-being and CV risk.**

854 In the 320 women randomized to treatment we will test the following hypotheses:

855 **H1A:** Women on active treatment will show a decreased Stress Reactivity composite score over  
856 12 months relative to baseline levels and relative to the change (increased stress reactivity) in  
857 women on placebo. If confirmed, the following parallel hypotheses will be examined in  
858 hierarchical order: Women on active treatment will show 1) a lower rate of metabolic risk; and 2)  
859 increased endothelial flow-mediated dilatation and baroreceptor sensitivity. These hypotheses  
860 will be tested as main effects of treatment.

861 **H1B:** A history of DEP will predict a greater effect of ERT on Stress Reactivity: i.e., a greater  
862 decrease in Stress Reactivity (relative to baseline) between active and placebo treated women  
863 will be seen in women with a history of DEP (due to their higher baseline reactivity) compared  
864 with never DEP women. If confirmed, the following parallel hypotheses will be examined in  
865 hierarchical order: a history of DEP will predict a greater effect of ERT for 1) reductions in rate  
866 of metabolic risk, and 2) increased endothelial flow-mediated dilatation and baroreceptor  
867 sensitivity. These hypotheses will be tested as interactive effects (history by treatment).

868 **H2:** Although no subjects will be depressed at baseline, active treatment will be associated with  
869 a lower proportion of women experiencing episodes of DEP over 12 months relative to placebo  
870 treated women. If confirmed, the following parallel hypotheses will be examined in hierarchical  
871 order: Active treatment will be associated with: 1) lower CES-D DEP scores; 2) decreased  
872 functional impairment; and 3) decreased affective instability.

873 **H3: Secondary Hypothesis:** Treatment-related reductions in Stress Reactivity will partially  
874 mediate the beneficial effect of E2 on DEP episodes. If confirmed, the following parallel  
875 hypotheses will be examined in hierarchical order: Treatment reductions in Stress Reactivity will  
876 partially mediate reductions in 1) CES-D DEP rating scores; 2) Functional Impairment; and 3)  
877 Affective Instability (tested with sensitivity analyses).

878 **DATA ANALYTIC PLAN FOR EACH HYPOTHESIS**

879 **Aim 1 Hypothesis 1:** Since subjects have not yet been assigned to treatment, we will treat  

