880 analyses of baseline data as two-group analyses rather than a main effect in a two-by-two  
881 factorial. The Stress Reactivity composite score as the response. If the null hypothesis is  
882 rejected, we will examine the same contrast for metabolic risk (as a parallel logistic regression  
883 model since it is categorical), flow mediated dilatation, and baroreceptor sensitivity.

884 **Aim 1 Hypothesis 2:** This secondary analysis will add the effect of trauma to the model, and  
885 assess whether trauma moderates the effect of DEP history on CV risk variables (above).

886 **Aim 2 Hypothesis 1:** In the mixed random coefficients model we will use for this repeated  
887 measures analysis, we will test this hypothesis using a contrast that examines the difference  
888 between the women with and without histories of DEP on the difference between the month 0  
889 and month 12 least squares means. This contrast will be done in the context of the full model but  
890 involves means from 2 of the 4 between-subjects cells. If this null hypothesis is rejected, we will  
891 test the same hypotheses for flow mediated dilatation and baoreceptor sensitivity (mixed model),  
892 and examine metabolic risk (categorical) via parallel logistic regression model.

893 **Aim 2 Hypothesis 2:** We will fit a two-factor logistic regression predicting the presence or  
894 absence of DEP episodes during the follow-up period. If we reject the null hypothesis, we will  
895 follow this with a two-factor mixed random coefficient model using CED-D, functional  
896 impairment and (using without the repeated measures portion since affective instability is  
897 defined over the entire follow-up period) affective instability as defined earlier. Further, as  
898 sensitivity analyses, we will examine the same effect on number of episodes / month during the  
899 follow-up period, using Poisson regression, and on the CES-D scores themselves using a mixed  
900 model.

901 **Aim 3 Hypothesis 1 (A and B):** With stress reactivity as the response, we will test these  
902 hypotheses in the context of the two between-factor one-repeated factor mixed random  
903 coefficient model we listed earlier. Hypothesis H1A is the main effect for treatment, predicting  
904 that the difference between the change in LSMs from month 0 to month 12 will be in different  
905 directions in the treated and untreated women. If this null hypothesis is rejected, we will examine  

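### Because secondary outcomes are examined only after the primary null is rejected, a null Stress Reactivity result leaves metabolic risk with no treatment estimate, and the gate's two wordings disagree about a harmful result

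*Protocol*

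**What the plan says.** The general rule is in the Multiple Testing paragraph, under General Statistical Considerations. The primary outcome of each hypothesis is tested without correction, and then "We will only examine other variables if the null" hypothesis for the primary is rejected. The stated purpose is to follow up and interpret significant effects.

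Aim 3 applies the rule to the randomised comparison.

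- **H1A (Specific Aims and Hypotheses).** Stress Reactivity is predicted to fall on estradiol relative to "women on placebo. If confirmed, the following parallel hypotheses will be examined in" "hierarchical order: Women on active treatment will show 1) a lower rate of metabolic risk; and 2") increased flow-mediated dilatation and baroreceptor sensitivity. The Data Analytic Plan restates the condition: "directions in the treated and untreated women. If this null hypothesis is rejected, we will examine" the other outcomes.
- **H2 (Specific Aims and Hypotheses).** Active treatment is predicted to lower the proportion with a depressive episode relative to placebo "treated women. If confirmed, the following parallel hypotheses will be examined in hierarchical" order: CES-D score, functional impairment, affective instability. The Data Analytic Plan again makes rejection of the null the condition.

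Under Cardiovascular Risk Measures, metabolic risk is a yes/no variable. It is positive on "metabolic syndrome based on any three of the following risk factors" (blood pressure, waist, triglycerides, HDL, fasting glucose) or on HOMA-IR above 3.2. Risks and Measures to Minimize Risks includes, among less frequent estradiol effects, "abdominal cramps, increased blood pressure, headache and worsening of migraines or asthma".

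**The concern.** A gate of this kind protects against false claims of benefit. Here it is written to decide whether an outcome is looked at, not only whether a benefit may be claimed, and it covers an outcome that could also move the wrong way.

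If Stress Reactivity is null, the plan as written gives no treatment estimate for metabolic risk. A reader of a null trial would still want to know whether 12 months of estradiol shifted blood pressure, triglycerides, HDL or glucose. The data to answer this will have been collected at baseline, month 6 and month 12.

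The opening condition is a separate problem. One wording needs a rejected null. The other needs confirmation of a hypothesis that has a stated direction. They part company when the primary is significant in the harmful direction.

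**Working it through.** **1. Can an ungated analysis stand in for metabolic risk?** The Stress Reactivity composite uses mean arterial pressure only as the difference between stress and rest. If estradiol raised both by the same amount c, then (stress + c) − (rest + c) = stress − rest, and the composite would not change. Lipids and glucose are not in it. No other arm comparison stated in the protocol contains clinic blood pressure, HDL, triglycerides or glucose.

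**2. The plan's own figures.** For H2 the protocol states power above 96% for 18.75% versus 37.5%, two-tailed 0.05, 240 subjects. Power = Φ[(|p1 − p2| − 1.96·se0)/se1], with se0 = √(2·p̄(1 − p̄)/n), se1 = √((p1q1 + p2q2)/n) and p̄ = 0.28125.

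- n = 120 per arm: (0.1875 − 1.96 × 0.0580)/0.0568 = 1.30, power 90.3%.
- n = 160 per arm: (0.1875 − 1.96 × 0.0503)/0.0492 = 1.81, power 96.5%.

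The stated figure therefore fits 320 subjects, not 240. That is a separate matter. Here it means that the H2 gate is shut 3.5% (320) to 9.7% (240) of the time at the planned effect.

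For Stress Reactivity the protocol gives power only for the depression-history contrast (effect sizes 0.63 and 0.40), not for treatment. The treatment effects below are therefore assumptions.

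**3. How often the H1A gate stays shut.** Inputs: 160 per arm; two-sided 0.05 (stated for H2, assumed for H1A); true benefit d in SD units. A two-sample normal comparison approximates the mixed model. SE = √(2/160) = 0.1118. P(significant benefit) = Φ(d/0.1118 − 1.96); P(significant harm) = Φ(−d/0.1118 − 1.96).

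| True benefit d | Significant benefit | Significant harm | Shut, null-rejected wording | Shut, confirmed wording |
|---|---|---|---|---|
| 0 | 2.5% | 2.5% | 95% | 97.5% |
| 0.1 | 14.3% | 0.2% | 85% | 86% |
| 0.2 | 43.2% | <0.1% | 57% | 57% |
| 0.3 | 76.5% | <0.1% | 23% | 23% |
| 0.4 | 94.7% | <0.1% | 5% | 5% |

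With 120 per arm, power is 34.1% at 0.2 SD and 87.3% at 0.4 SD, so the gate is shut about 66% and 13% of the time. At zero effect it is 95% at any sample size.

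**4. Where the two wordings diverge.** Reverse the sign of d. If estradiol truly worsened reactivity by 0.2 SD, the null-rejected wording would open the gate about 43% of the time; at 0.4 SD, about 95%. Under the confirmed wording it would almost never open (below 0.1%).

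**5. The mood side.** A depressive episode is defined as CES-D of 16 or more, and the proportion with an episode is compared between arms in every case. With placebo at 37.5% and 160 per arm, an assumed rise on estradiol to 45%, 50% or 55% would be significant in the harmful direction 27%, 62% or 88% of the time. What stays gated is the CES-D score as a continuous measure and SF-36 function.

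**The case against.** The strongest defence is that this is ordinary hierarchical testing of efficacy outcomes, in a paragraph about multiplicity that nowhere claims to govern safety reporting. The protocol's rationale treats estradiol as beneficial for metabolic risk. It lists raised blood pressure only among less frequent effects, and it names hypertension and hyperlipidemia as conditions likely to emerge in perimenopausal women, not as estradiol effects. Several safety routes are ungated: the DSMB, adverse event grades that include Stage 2 hypertension and mood worsening, monthly aggregate review, and blood pressure and LDL surveillance. H1B also gives a second way to reach metabolic risk; with both nulls true and independence assumed, at least one gate opens 1 − 0.95² = 9.75% of the time.

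Much of this stands, and it limits the point. It does not remove it. The rule says *examine*, so an analysis plan that reported metabolic risk by arm after a null primary would depart from the protocol. The ungated routes work through individual thresholds and aggregate reports, with no stated arm estimate, so a shift below a threshold need not appear. H1B concerns the history-by-treatment interaction, not the overall treatment effect.

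Four stronger readings are tempting, and the document does not support them.

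- *Worsened mood would go unreported.* The H2 primary is built from the CES-D and always tested, and CES-D scores of 10 to 15 are graded as a moderate adverse event.
- *Harm would usually be missed.* That depends on the true effect on reactivity, which the protocol does not give.
- *The gate probability can be multiplied by power to give a chance of detecting harm.* Metabolic risk is binary and no rate for it is stated. On the mood side, gate and outcome share one scale, so independence fails.
- *LDL and visit-level blood pressure tables are missing.* An analysis plan that is not at hand could supply them.

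**Conclusion.** The point holds in a limited form. As written, the protocol makes the treatment estimate for metabolic risk conditional on a significant Stress Reactivity result, and nothing else it plans to compare between arms carries the same information. The size depends on an effect that the protocol does not state: the H1A gate is shut 95% of the time at zero, about 57% at 0.2 SD and about 5% at 0.4 SD. This assumes 160 per arm, two-sided 0.05 and a normal approximation. For CES-D severity and SF-36 function the consequence is smaller. The conflict between the two opening conditions does not depend on any assumed effect. This is a cheap improvement in wording and reporting; it is not a flaw in the primary tests.

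**What to change.** Three changes:

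1. In Multiple Testing, say that the gate governs confirmatory claims of benefit.
2. Add that treatment differences with 95% confidence intervals will be reported by arm, whatever the primary result, for metabolic risk and its collected components (clinic blood pressure, waist, triglycerides, HDL, fasting glucose, HOMA-IR), CES-D total score and SF-36, labelled as not multiplicity-controlled.
3. Use one opening condition in Multiple Testing, Specific Aims and Hypotheses, and the Data Analytic Plan, and say what follows when the primary is significant in the harmful direction.

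The data are already collected. The primary tests and their significance level are untouched. The cost is a few more estimates without multiplicity control, some of which may look notable by chance and must be read as such.
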